6.4. Guidelines for Ibrutinib Management with Surgeries or Procedures

Ibrutinib may increase risk of bleeding with invasive procedures or surgery. The following guidance should be applied to the use of ibrutinib in the perioperative period for subjects who require surgical intervention or an invasive procedure while receiving ibrutinib.

6.4.1. Minor Surgical Procedures

For minor procedures (such as a central line placement, skin or needle biopsy, lumbar puncture [other than shunt reservoir access], thoracentesis, or paracentesis) ibrutinib should be held for at least 3 days prior to the procedure and should not be restarted for at least 3 days after the procedure. For bone marrow biopsies that are performed while the subject is on ibrutinib, it is not necessary to hold ibrutinib.

6.4.2. Major Surgical Procedures

For any surgery or invasive procedure requiring sutures or staples for closure, ibrutinib should be held at least 7 days prior to the intervention (except for emergency procedures) and should be held at least 7 days after the procedure and restarted at the discretion of the investigator when the surgical site is reasonably healed without serosanguinous drainage or the need for drainage tubes.

7. STUDY EVALUATIONS

7.1. Description of Procedures

7.1.1. Assessments

7.1.1.1. ICF

The subject must read, understand, and sign the Institutional Review Board/Research Ethics Board/Independent Ethics Committee (IRB/REB/IEC) approved ICF confirming his or her willingness to participate in this study before any study-specific screening procedures are performed. Subjects in the US must also grant permission to use protected health information per the Health Insurance Portability and Accountability Act (HIPAA). In addition, subjects must sign all approved ICF amendments per the site IRB/REB/IEC guidelines during the course of the study.

7.1.1.2. Confirm Eligibility

All necessary procedures and evaluations must be performed to document that the subject meets all of the inclusion criteria and none of the exclusion criteria until first dose of study drug ([Section 4](#)).

7.1.1.3. Medical History and Demographics

The subject's relevant medical history through review of medical records and by interview will be collected and recorded. Concurrent medical signs and symptoms must be documented to establish baseline severities.

7.1.1.4. Prior and Concomitant Medications

All medications at least 14 days prior to first dose through 30 days after the last dose of study drug will be documented.

7.1.1.5. Adverse Events

The accepted regulatory definition for an adverse event (AE) is provided in [Section 11.1](#). The occurrence of an AE at the time the ICF is signed until first dose should be recorded under medical history in the eCRF form. All medical occurrences after the first dose with study drug

until 30 days after the last dose of study drug that meet the AE definition below must be recorded as AEs in the CRF.

- Grade 1 adverse events do not need recorded
- Grade 2 unexpected **and** possibly/probably/definitely related
- Grade 3 requiring hospitalization **and** unexpected/expected regardless of relationship
- Grade 3 unexpected without hospitalization **and** possibly/probably/definitely related
- All grades 4 & 5 regardless of unexpected/expected or relationship

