Objectives:	
Primary Objective:
 
Efficacy The primary endpoint is to estimate the proportion of patients that are alive and off systemic immunosuppression therapies (IST) at 12 months following initiation of treatment. To meet this endpoint, patients need to remain off IST (e.g. sirolimus, tacrolimus, steroids, etc). for at least 8 weeks. The use of rituximab and ibrutinib are not considered IST for this endpoint.
 
Secondary Objectives:
 
Efficacy
 
To estimate:
 
 1. Chronic GVHD response (CR + PR, both individual organ response and overall response, according to 2014 NIH Response Criteria Working Group Report) – See Appendix G. 2. Cumulative steroid exposure (total mg methylprednisolone or equivalent). 3. Time to discontinuation of systemic immunosuppression, defined as the date that all systemic IST such as sirolimus, tacrolimus, steroids, etc. have been discontinued after resolution of all reversible manifestations of cGVHD. The use of rituximab and ibrutinib are not considered IST for this endpoint. Discontinuation of immunosuppressive medications for the purpose of inducing an anti-tumor response after the development of recurrent or secondary malignancy will not be counted as successful discontinuation of IST.

	
 4. Failure-free survival (defined as being alive without the requirement for second-line cGVHD therapy). See section 6.3 for definition of second-line cGVHD therapy. 5. Non-relapse and overall mortality 
Safety
 
To estimate:
 
 1. Incidence of grade ≥ 3 adverse events, possibly or probably related to either ibrutinib and/or rituximab.
Study Design:	This is an open-label, Phase 2 study designed to evaluate the safety and efficacy of ibrutinib and rituximab as primary treatment of cGVHD.
Population:	35 patients
Centers:	One

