8.2.2. Response Follow-up

Required testing for the response follow-up visits (months 1, 2, 3, 6, 9, 12):

- Medical history
- Physical examination, including vital signs, weight, and Karnofsky performance status
- Laboratory evaluation per institutional guidelines including CBC with differential, glucose, BUN, creatinine, total bilirubin, alkaline phosphatase, LDH, albumin, SGOT(AST), SGPT (ALT), CRP, CK, calcium, and magnesium.
- Biomarkers (correlative lab studies)
- Documentation of concomitant medications
- Completion of institutional GVHD assessment form (see Appendix E)
- Completion of a GVHD patient self-report form (see Appendix F)
- Document cumulative corticosteroid use
- Document any new systemic IST and reason for use

- Document treatment-emergent toxicities and adverse events
- Document any IVIG use
- PFTs (at 3, 6, 9 and 12 month visits only)

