10.2.2. Secondary Endpoints

Secondary efficacy endpoints:

To estimate:

- Chronic GVHD response (CR + PR, both individual organ response and overall response, according to 2014 NIH Response Criteria Working Group Report) – See Appendix G.
- Cumulative steroid exposure (total mg methylprednisolone or equivalent).
- Time to discontinuation of systemic immunosuppression (defined as the date that all systemic IST has been discontinued after resolution of all reversible manifestations of cGVHD. Discontinuation of immunosuppressive medications for the purpose of inducing an anti-tumor response after the development of recurrent or secondary malignancy will not be counted as successful discontinuation of IST).
- Failure-free survival (defined as being alive without the requirement for second-line cGVHD therapy). See section 6.3 for definition of second-line cGVHD therapy.
- Non-relapse and overall mortality

Safety endpoints:

To estimate:

- Incidence of grade ≥ 3 adverse events, possibly or probably related to either ibrutinib and/or rituximab.

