11.2. Unexpected Adverse Events

An "unexpected" AE is an AE that is not listed in the IB or is not listed at the specificity or severity that has been observed. For example, hepatic necrosis would be "unexpected" (by virtue of greater severity) if the IB referred only to elevated hepatic enzymes or hepatitis. Similarly, cerebral thromboembolism and cerebral vasculitis would be "unexpected" (by virtue of greater specificity) if the IB listed only cerebral vascular accidents. "Unexpected" also refers to AEs that are mentioned in the IB as occurring with a class of drugs or as anticipated from the pharmacological properties of the drug, but are not specifically mentioned as occurring with the study drug under investigation.

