11.4. Documenting and Reporting of Adverse Events and Serious Adverse Events by Investigators

11.4.1. Assessment of Adverse Events

Investigators will assess the occurrence of AEs and SAEs at all subject evaluation time points during the study. All AEs and SAEs whether volunteered by the subject, discovered by study personnel during questioning, detected through physical examination, clinically significant laboratory test, or other means, will be recorded in the subject's medical record and on the AEs CRF and, when applicable, on the Serious Adverse Event Report Form.

Each recorded AE or SAE will be described by its duration (i.e., start and end dates), severity, regulatory seriousness criteria (if applicable), suspected relationship to the investigational product, and any actions taken.

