11.4.2. Adverse Event Reporting Period

All AEs whether serious or non-serious, will be documented from the time signed and dated ICF is obtained until 30 days following the last dose of study drug or the start date of a new therapy for cGVHD. SAEs will be reported to the Sponsor Drug Safety via an SAE reporting form and will be recorded in the CRF from the time of ICF signing. Non-serious AEs will be recorded in the source documents from the time of ICF signing and will be recorded in the CRF from the first dose of study drug(s).

SAEs reported after 30 days following the last dose of study drug should also be reported if considered related to study drug. Resolution information after 30 days should be provided.

Progressive disease should NOT be reported as an event term, but instead symptoms/clinical

signs of disease progression may be reported. (See [Section 11.1.1](#))

All AEs, regardless of seriousness, severity, or presumed relationship to study drug, must be recorded using medical terminology in the source document. All records will need to capture the details of the duration and the severity of each episode, the action taken with respect to the study drug, investigator's evaluation of its relationship to the study drug, and the event outcome. Whenever possible, diagnoses should be given when signs and symptoms are due to a common etiology (e.g., cough, runny nose, sneezing, sore throat, and head congestion should be reported as "upper respiratory infection"). Investigators must record in the CRF their opinion concerning the relationship of the AE to study therapy. All measures required for AE management must be recorded in the source document and reported according to Sponsor instructions.

All deaths should be reported with the primary cause of death as the AE term, as death is typically the outcome of the event, not the event itself. Autopsy and postmortem reports must be forwarded to the Sponsor, or designee, as outlined above, if allowed per local regulatory guidelines.

If a death occurs within 30 days after the last dose of study drug, the death must be reported to the Sponsor as a SAE.

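### The CRF rule in section 7.1.1.5 omits expected, related, non-hospitalized Grade 3 events that the safety endpoint counts, conflicts with 11.4.1 and 11.4.2, and uses causality terms that are not on the 11.1.4 scale

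*Combined protocol and SAP*

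**What the plan says.** **Endpoint.** The synopsis, section 2.2 and section 10.2.2 give the same safety endpoint: the incidence of Grade 3 or higher "adverse events, possibly or probably related to either ibrutinib and/or rituximab". It has no condition on expectedness or hospitalization.

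**CRF rule in section 7.1.1.5.** From first dose to 30 days after last dose, the section requires CRF entry for events meeting a list of criteria. Grade 1 is exempt. Grade 2 is entered if unexpected and related. Grade 3 with hospitalization is always entered. Otherwise the only Grade 3 line is "Grade 3 unexpected without hospitalization", and the event must also be judged possibly, probably or definitely related. Grades 4 and 5 are always entered.

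**CRF rule in section 11.** Section 11.4.1 says that all AEs and SAEs "will be recorded in the subject's medical record and on the AEs CRF". Section 11.4.2 sends non-serious AEs to the CRF from first dose. Neither filters by grade, expectedness or relationship. For source documents, 11.4.2 adds: "All AEs, regardless of seriousness, severity, or presumed relationship to study drug, must be recorded using medical terminology in the source document". Section 8.2.2 lists "Document treatment-emergent toxicities and adverse events" at each response visit, also unfiltered.

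**Expectedness.** Under section 11.2 an event is unexpected if it is absent from the Investigator's Brochure or "is not listed at the specificity or severity that has been observed".

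**Causality.** The section 11.1.4 scale has four categories: *Not Related*, *Unlikely*, *Possibly Related* and *Related*.

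**The concern.** An endpoint can only be computed from what reaches the analysis data. Here one section narrows what must be entered, another does not, and no text ranks them. Two people following the same protocol could build different CRF datasets and report different values for the one safety endpoint in 10.2.2. Events lost this way can only lower the reported incidence.

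The affected category is realistic. Section 1.2.1.3 itself reports Grade 3 or 4 cytopenias with ibrutinib, so a Grade 3 cytopenia managed without admission could be classed as expected. Section 5.1.1.4 makes some Grade 3 toxicities a reason for a dose change and requires the change in the CRF. Under 7.1.1.5 the CRF could then show the change without the event behind it.

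The plan also compares safety with the historical rituximab experience (sections 2.2 and 10.4). The documents give no AE recording rule for that earlier trial, so the direction of any bias in the comparison cannot be established.

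The causality wording is a second, smaller problem. An investigator using the 11.1.4 scale cannot record an event as probably or definitely related, and the endpoint does not name the scale's top category.

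**Working it through.** The plan states no figure on this point, so the check is a comparison of text followed by an illustration.

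**Step 1. Events that count for the endpoint, against the two CRF rules** (all rows are events judged related)

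| Event | In endpoint (10.2.2) | On 7.1.1.5 list | CRF under 11.4.1 and 11.4.2 |
|---|---|---|---|
| Grade 3, hospitalized | Yes | Yes | Yes |
| Grade 3, not hospitalized, unexpected | Yes | Yes | Yes |
| Grade 3, not hospitalized, expected | Yes | **No** | Yes |
| Grade 4 or 5 | Yes | Yes | Yes |

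One cell that the endpoint needs is missing from 7.1.1.5, and in that cell the two rules differ.

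**Step 2. Other routes to capture.** SAEs are recorded in the CRF under 11.4.2. They include important medical events without hospitalization (11.1.2). Hemorrhage of Grade 3 or higher goes on the SAE form whether or not it is serious (11.4.6 and 11.4.6.1). What remains is the expected, related Grade 3 event that is non-serious and non-hemorrhagic. It should be in source, but the plan describes no step that brings non-CRF events into the analysis.

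**Step 3. Causality terms**

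| Place | Terms that count as related |
|---|---|
| Synopsis, 2.2, 10.2.2 | possibly, probably |
| 7.1.1.5 | possibly, probably, definitely |
| 11.1.4 (scale the investigator uses) | *Possibly Related*, *Related* |

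Only the *possibly* level appears in all three. Read literally, the endpoint leaves out *Related*.

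**Step 4. Size.** Let T be the number of patients with at least one related Grade 3 or higher event. Let k be the number whose only such events fall in the residual gap of step 2. With the planned 35 patients (section 10.3):

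reported incidence = (T − k)/35, and each such patient costs 1/35 = 0.0286, or 2.9 percentage points.

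T and k are assumptions, because the documents give no event rate.

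| True T | k = 0 | k = 1 | k = 3 | k = 5 |
|---|---|---|---|---|
| 7 (20.0%) | 7/35 = 20.0% | 6/35 = 17.1% | 4/35 = 11.4% | 2/35 = 5.7% |
| 14 (40.0%) | 14/35 = 40.0% | 13/35 = 37.1% | 11/35 = 31.4% | 9/35 = 25.7% |
| 21 (60.0%) | 21/35 = 60.0% | 20/35 = 57.1% | 18/35 = 51.4% | 16/35 = 45.7% |

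A patient with any other recorded related event of Grade 3 or higher still counts, so k may be zero.

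**The case against.** The strongest reply is that the sections can be obeyed together. Section 7.1.1.5 says what must be entered and expressly exempts only Grade 1. It does not forbid entering an expected Grade 3 event, and a site that also follows 11.4.1 and 11.4.2 would enter it. This is right as far as it goes: the undercount arises only where 7.1.1.5 is read as the complete list. But that is a natural reading of a list with such specific conditions, and if section 11 governs, the list has no function. Nothing in the text settles it.

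The cytopenia example has limits. Expectedness depends on the Investigator's Brochure, which is not among the documents. Platelets from 30 × 10⁹/L are eligible (4.1), while 5.1.1.4 gives Grade 3 thrombocytopenia as below 50,000/µL. Some patients may therefore enter at Grade 3, and a pre-existing condition is not an AE unless it worsens (11.1.1). Scheduled blood counts would also leave a laboratory record, though without attribution. And the specific cytopenia triggers in 5.1.1.4 are Grade 4 events or Grade 3 thrombocytopenia with bleeding, so the dose-change argument applies mainly to other Grade 3 toxicities. All of this stands; it narrows the gap without closing it.

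The values of T and k are hypothetical, and the most extreme (5 of 7) has no support in the documents. That also stands. The table shows sensitivity and is not an estimate.

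On causality, few readers would take the endpoint to exclude clearly related events. This part is mainly terminology.

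Finally, the endpoint strictly needs only one added line, for expected, related, non-hospitalized Grade 3 events. That would close the gap. Requiring all Grade 3 or higher events goes slightly further, but it agrees with section 11 and removes expectedness and attribution as filters at data entry.

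**Conclusion.** The concern holds. The list in 7.1.1.5 leaves out one category of event that the endpoint includes, it conflicts with 11.4.1 and 11.4.2, and no text says which prevails. Confidence is high for the textual mismatch. The resulting undercount is conditional: it requires that 7.1.1.5 be applied as the full CRF rule and that some patients have qualifying events only in the gap. Its size is unknown and may be zero, at 2.9 percentage points per such patient among 35. The missing events should be recoverable from source.

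The causality mismatch is real but minor, and no number is attached to it. The point should be fixed. It does not touch the primary endpoint, but it affects the only safety endpoint listed in 10.2.2, in a trial whose title names safety.

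**What to change.** 1. **Section 7.1.1.5.** Replace the two Grade 3 bullets and the Grade 4 and 5 bullet with one line: *All Grade 3 or higher AEs, regardless of expectedness, hospitalization or relationship.* State that this is the minimum CRF requirement.
2. **Sections 11.4.1 and 11.4.2.** Reconcile them with 7.1.1.5 and say which rule governs CRF entry, including for Grades 1 and 2. Do not reduce the capture of Grade 3 or higher events or SAEs that section 11 already requires.
3. **Synopsis, 2.2 and 10.2.2.** Define the endpoint as Grade 3 or higher AEs assessed as *Possibly Related* or *Related* to ibrutinib and/or rituximab. Use the same two terms in 7.1.1.5. Expanding the 11.1.4 scale would also work, provided that one scale is used throughout and the categories that count as related are named.

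The cost is a wording amendment and some additional CRF entries for Grade 3 events. Section 11.4.2 already requires all AEs in source, so no new assessment is needed.

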7.1.1.6. Physical Examination

The Screening and follow-up visit physical examination will include, at a minimum, the general appearance of the subject, height (screening only) and weight, and examination of the skin, eyes, ears, nose, throat, lungs, heart, abdomen, extremities, musculoskeletal system, nervous system, and lymphatic system.

7.1.1.7. Karnofsky Performance Status (KPS)

The KPS performance index is provided in [Appendix B](#).

7.1.1.8. Vital Signs

Vital signs will include blood pressure, heart rate, respiratory rate and body temperature.

7.1.2. Laboratory

Laboratory evaluation will be performed per institutional guidelines and include CBC with differential, glucose, BUN, creatinine, total bilirubin, alkaline phosphatase, albumin, SGOT(AST), SGPT (ALT), magnesium and calcium. Relevant immunosuppressive drug levels (e.g. sirolimus) will be checked per institutional guidelines.

7.1.3. Diagnostics/Procedures

Radiology (e.g. plain films, CT), pulmonary function tests (PFTs), biopsies (e.g. skin, liver, GI tract) will be performed according to institutional standards.

7.2. Efficacy Evaluations

Formal efficacy assessments will be performed at baseline and post-treatment, monthly x 3 (1, 2, and 3 months), then q3months x 3 (6, 9, and 12 months). See section 8.2.2 for detailed study assessments. All other assessments will be done at the physician's discretion or institutional standards.

7.3. Correlative Blood Collection and Handling

Research blood samples (30-60ml) will be drawn at baseline, prior to ibrutinib dosing, and at each study visit (month 1, 2, 3, 6, 9, 12) for a total of 7 samples. From each blood sample, peripheral blood mononuclear cells (PBMCs) and serum will be collected and cryopreserved for correlative studies.

At each timepoint:

- Serum – draw 10 ml of serum
- PBMCs – If ALC \geq 1000/ μ l, draw 30ml. If ALC $<$ 1,000/ μ l, draw 50ml

Samples will be frozen in -80° C or liquid nitrogen.

8. STUDY PROCEDURES

(See Appendix A for details regarding timing of study procedures and testing.)

8.1. Screening Phase

8.1.1. Screening/Consenting Visit

Required testing for the screening visit:

- Medical History
- Physical examination with vital signs, height, weight
- Schirmer's Test
- Karnofsky Performance Status (Appendix B)
- Serum Pregnancy test
- Hepatitis Serologies (HepBsAg, HepBsAB, HepC)
- Fasting lipid panel
- Laboratory evaluation per institutional guidelines including CBC with differential, glucose, BUN, creatinine, total bilirubin, alkaline phosphatase, LDH, albumin, SGOT(AST), SGPT (ALT), CRP, CK, calcium, and magnesium.
- IgG level
- Biomarkers (correlative lab studies)

- Pulmonary Function Test
- GVHD assessment form (Appendix E)
- GVHD self-report form (Appendix F)

Eligibility criteria will be verified, and ineligible patients will proceed off study and no further follow-up will be obtained.

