1.2.1.2. Infections

Infections (including sepsis, bacterial, viral, or fungal infections) were observed in subjects treated with ibrutinib. Some of these infections have been associated with hospitalization and death. Consider prophylaxis according to standard of care in subjects who are at increased risk for opportunistic infections (reference [Section 6.1](#)). Although causality has not been established, cases of progressive multifocal leukoencephalopathy (PML) and hepatitis B reactivation have occurred in subjects treated with ibrutinib. Subjects should be monitored for signs and symptoms (fever, chills, weakness, confusion, vomiting and jaundice) and appropriate therapy should be instituted as indicated.

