4.2. Exclusion Criteria

To be enrolled in the study, potential subjects must meet NONE of the following exclusion criteria:

1. Patients with late persistent or recurrent acute GVHD
2. Active uncontrolled infection
3. History of HIV infection
4. Active HBV or HCV infection. Subjects who are positive for hepatitis B core antibody, hepatitis B surface antigen (HBsAg), or hepatitis C antibody must have a negative polymerase chain reaction (PCR) result before enrollment. Those who are PCR positive will be excluded.
5. Inability to tolerate oral medications.
6. Progressive or recurrent malignancy following allogeneic transplant
7. Known severe or life-threatening hypersensitivity to ibrutinib or rituximab
8. Creatinine > 2 mg/dl or calculated CrCl < 30ml/min
9. Requirement for anticoagulation therapy
10. Uncontrolled hypertension
11. Known bleeding disorder
12. Major surgery within 4 weeks of first dose of study drug
13. History of stroke or intracranial hemorrhage within 6 months prior to enrollment
14. Unable to swallow capsules
15. Subjects with chronic liver disease and hepatic impairment meeting Child-Pugh Class C (Appendix D).
16. Female subjects who are pregnant, or breastfeeding, or planning to become pregnant while enrolled in this study or within 90 days of last dose of study drug. Male subjects who plan to father a child while enrolled in this study or within 90 days after the last dose of study drug.
17. Unwilling or unable to participate in all required study evaluations and procedures
18. Unable to understand the purpose and risks of the study and to provide a signed and dated informed consent form (ICF) and authorization to use protected health information (in accordance with national and local subject privacy regulations)
19. Exposure to BTK inhibitor following transplant. Prior exposure to BTK inhibitor pre-transplant is allowed.
20. Vaccinated with live, attenuated vaccines within 4 weeks of first dose of study drug
21. Unresolved toxicities from prior anticancer therapy, defined as having not resolved to Common Terminology Criteria for Adverse Event (CTCAE, v5.0), Grade ≤ 1 , or to the levels dictated in the inclusion/exclusion criteria with the exception of alopecia

-
- 22. Any life-threatening illness, medical condition, or organ system dysfunction that, in the investigator's opinion, could compromise the subject's safety or put the study outcomes at undue risk

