5.1.2.4. Dose Modification for Adverse Reactions

The dose of rituximab generally remains constant throughout the trial. Rituximab infusion should be interrupted for severe reactions, e.g., rapid tumor lysis. Treatment of infusion-related symptoms with diphenhydramine and acetaminophen is recommended. Additional treatment with bronchodilators or IV saline may be indicated. Epinephrine, antihistamines, and corticosteroids should be available for immediate use in the event of a hypersensitivity reaction to rituximab (e.g., anaphylaxis). In most cases, the infusion can be resumed at a 50% reduction in rate (e.g., from 100mg/hr to 50mg/hr) when symptoms and laboratory abnormalities have completely resolved.

Infusions should be discontinued in the event of serious or life-threatening cardiac arrhythmias. Subjects who develop clinically significant arrhythmias should undergo cardiac monitoring during and after subsequent infusions.

Subjects who meet the following criteria should be discontinued from the study:

- Active HBV infection or hepatitis
- Severe or life-threatening anaphylaxis or hypersensitivity reaction

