14. APPENDICES

Appendix A. Schedule of Assessments

Study Day	Screening (within 7 days)	Day 1	Day 7 (+/- 3 days)	Month 1 (+/- 7 days)	Month 2 (+/- 7 days)	Month 3 (+/- 7 days)	Month 6 (+/- 7 days)	Month 9 (+/- 7 days)	Month 12 (+/- 7 days)
Informed Consent	X								
Eligibility Confirmation	X								
Ibrutinib 420mg daily ¹		X		Continuous daily dosing Dispensed on D1 of each cycle through Cycle 12					
Rituximab 375mg/m ²			X ²					X ³	
Medical History	X			X	X	X	X	X	X
Physical Exam w/vitals	X			X	X	X	X	X	X
Schirmer's test	X			X	X	X	X	X	X
Karnofsky Performance Status	X								
Serum Pregnancy	X								
Hepatitis serologies	X								
Fasting Lipid Panel	X								
CBC w/differential	X	X	X	X	X	X	X	X	X
Comprehensive Metabolic Panel ⁴	X	X	X	X	X	X	X	X	X
IgG level	X					X	X	X	X
CRP	X			X	X	X	X	X	X
CK	X			X	X	X	X	X	X
LDH	X			X	X	X	X	X	X
Biomarkers (Correlative studies)	X			X	X	X	X	X	X
Concomitant Medications	X			X	X	X	X	X	X
GVHD assessment ⁵	X			X	X	X	X	X	X
GVHD patient self-report form ⁶	X			X	X	X	X	X	X
Pulmonary Function Test	X					X	X	X	X
Calculate cumulative steroid dose				X	X	X	X	X	X
Any new systemic IST				X	X	X	X	X	X
Any IVIG therapy				X	X	X	X	X	X
Adverse Event				X	X	X	X	X	X

¹Dose reduction required when using strong Cyp 3A4 inhibitors (e.g. voriconazole or posaconazole, see Section 6.2.1, table 4) or with hepatic impairment (see Section 5.1.1.5, table 3).

²Rituximab induction 375mg/m² Q7days x 4 doses.

³Rituximab maintenance 375mg/m² q 3months (+/-7days) x 4 doses.

⁴Glucose, BUN, creatinine, total bilirubin, alkaline phosphatase, albumin, SGOT (AST), SGPT (ALT), calcium, magnesium

⁵See appendix E

⁶See appendix F

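### The required screening panel omits hepatitis B core antibody, one of the three markers that exclusion 4 uses to trigger a PCR before enrollment

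*Combined protocol and SAP*

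**What the plan says.** Exclusion 4 in section 4.2 sets the rule: "Subjects who are positive for hepatitis B core antibody, hepatitis B surface antigen (HBsAg), or hepatitis C antibody must have a negative" PCR result before enrollment, and "Those who are PCR positive will be excluded". The synopsis repeats it with the same three markers.

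Section 8.1.1, under its heading for required screening tests, itemises the panel as "Hepatitis Serologies (HepBsAg, HepBsAB, HepC". Appendix A has one row, "Hepatitis serologies", marked at screening only, with no markers named and no footnote.

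Two general clauses also bear on the point. Section 7.1.1.2 says that all necessary procedures "must be performed to document that the subject meets all of the inclusion criteria and none of the exclusion criteria". Section 8.1.1 closes with "Eligibility criteria will be verified, and ineligible patients will proceed off study".

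The protocol treats hepatitis B as a risk with both drugs. Section 1.2.1.2 records, with causality not established, that "cases of progressive multifocal leukoencephalopathy (PML) and hepatitis B reactivation have occurred in subjects treated with ibrutinib". Section 5.1.2.4, on rituximab, gives "Active HBV infection or hepatitis" as a reason to discontinue a subject from the study.

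**The concern.** The eligibility rule and the list of tests that would let staff apply it name different markers. Core antibody is in the rule and not in the list; surface antibody is in the list and not in the rule. Section 8.1.1 is the only place where the hepatitis panel is itemised, so it is the natural source for a screening order set.

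What is at stake is patient safety. A patient who is core-antibody positive but negative for surface antigen and hepatitis C shows nothing on the listed panel that would prompt a PCR. If that patient carries HBV DNA, the protocol intends exclusion. Instead the patient could receive an anti-CD20 antibody and a BTK inhibitor, with sirolimus or another immunosuppressant and possibly a short steroid course (section 3.1).

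**Working it through.** The plan states no figure to reproduce, so the check is a comparison of texts.

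**Markers side by side**

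| Marker | PCR trigger in exclusion 4 | Listed in 8.1.1 |
|---|---|---|
| Hepatitis B core antibody | Yes | **No** |
| Hepatitis B surface antigen | Yes | Yes |
| Hepatitis C antibody | Yes | Yes (HepC, read as antibody because it sits under serologies) |
| Hepatitis B surface antibody | No | Yes |

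Triggers covered: 2 of 3. Listed tests that exclusion 4 does not use: 1 of 3.

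**Which patients the list misses.** Three markers, each positive or negative, give 2³ = 8 result patterns. At least one trigger is positive in 8 − 1 = 7. The listed panel shows a positive surface antigen or hepatitis C result in 8 − 2 = 6. The one missed pattern (7 − 6 = 1) is core antibody positive with the other two negative. This only identifies the pattern; the patterns are not equally common, and the count is not a risk estimate.

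**Whether another section fills the gap**

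- Section 7.1.2 (laboratory): blood count, chemistry and drug levels; no hepatitis test.
- The general laboratory line in 8.1.1: no hepatitis test.
- Section 8.2.1.1 (cycle 1, day 1): blood count and metabolic panel, with blood count and hepatic function criteria verified; no serology.
- Section 8.2.2 (follow-up): liver tests at months 1, 2, 3, 6, 9 and 12; no HBV serology or PCR.
- Appendix A: the generic row only. It does not contradict 8.1.1 and does not add to it.
- Section 7.1.1.2 and the last line of 8.1.1: eligibility must be verified; no hepatitis marker named.

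No section schedules core antibody by name.

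**Who would be wrongly enrolled.** Only patients in the missed pattern who are also PCR positive. PCR-negative patients in that pattern are eligible; for them the consequence is a skipped required step.

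**The case against.** The strongest reply is that section 7.1.1.2 is binding. Core-antibody status is an explicit part of exclusion 4 and cannot be documented without a result, so a site that runs only the listed panel is already departing from the protocol. On this reading 8.1.1 merely fails to restate a requirement. It is also not a complete list of eligibility tests: exclusion 15 relies on the Child-Pugh score, whose PT/INR component (Appendix D) appears in neither 8.1.1 nor Appendix A. The surface-antibody entry may simply be a slip for core antibody, since eligibility uses surface antibody nowhere.

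There are later safeguards too. Appendix A schedules bilirubin, AST and ALT at screening, day 1 and day 7, when rituximab starts, as well as at the follow-up visits. Section 1.2.1.2 asks for monitoring of symptoms, including jaundice.

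Much of this stands as mitigation. A careful site may well order core antibody, so a missed PCR is possible rather than certain. It does not remove the inconsistency. A general duty that names no test sits beside a specific list that names the wrong one, and staff who follow the list would have no core-antibody result to act on. A slip would still need correcting, because the text as written means surface antibody. Liver tests do not replace the screening marker, and they are a weak signal in this population: liver involvement is itself a scored feature of cGVHD (Appendices E and G), inclusion 7 admits bilirubin up to 3.0 × ULN when due to cGVHD, and section 4 sets no AST or ALT limit.

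**Conclusion.** The concern holds. This is an internal inconsistency between an eligibility criterion and the screening list, and it should be corrected on safety grounds. One of the three PCR triggers is not in the only itemised panel, and patients positive for that marker alone are the ones missed.

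The conclusion rests on reading HepBsAB as surface antibody and HepC as hepatitis C antibody. The harm is conditional on staff running only the listed panel. The documents give neither the prevalence of core antibody nor the PCR-positive fraction among carriers, so no count can be given; in a one-center study of 35 patients it may be small or zero. Sample size, primary endpoint and analysis are not affected.

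**What to change.** - In section 8.1.1, add hepatitis B core antibody to the panel, in place of surface antibody or alongside it.
- In Appendix A, name the markers in the hepatitis row or in a footnote.
- State in both places that a positive core antibody or surface antigen requires a negative HBV PCR, and a positive hepatitis C antibody a negative HCV PCR, before enrollment.

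The cost is a short amendment and one extra assay on the blood already drawn at screening. The PCR adds no new requirement, because exclusion 4 already demands it of anyone with a positive trigger marker.
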